3.2 Study Duration, Enrollment and Number of Subjects

Enrollment will continue until 18 subjects have been enrolled who require an increase in PEEP of at least 5 cm H₂O (based on P_{tp} at the time of enrollment). Based on a prior study which found 29% of participants were within 5 cm H₂O of optimal PEEP at the time of enrollment (2), we expect we will need to measure esophageal pressures on approximately 25 patients to find 18 patients who require titration of PEEP. Based on expected enrollment of 2-4 participants per month, the trial is expected to complete enrollment within 12 months. Each patient’s participation will last 1 hour; for the few patients who remain on higher PEEP per the request of the team, safety monitoring will continue for an additional 24 hours.

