4.4 Post-Intervention

Measurements of ICP, CPP, and MAP will be repeated 5 minutes after the change in PEEP.

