5 STUDY EVALUATIONS AND MEASUREMENTS

	Pre-Intervention	Post-Intervention	Hourly x 24 Hours*
ICP	X	X	X
CPP	X	X	X
MAP	X	X	X
HR	X	X	X
SpO ₂	X	X	X
FiO ₂	X	X	X
PEEP	X	X	X
P _{tp}	X	X	
P _{aw}	X	X	
P _{es}	X	X	
Age	X		
BMI	X		
Diagnosis	X		

*Hourly data collected in patients who are continued on "optimal PEEP at the discretion of the primary team.

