6 STATISTICAL CONSIDERATION

6.1 Primary Endpoint

The primary endpoint is change in ICP 5 minutes after PEEP titration. the parameter representing mean increase during/after titration is > 4 (mm Hg) in the target population.

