6.3 Statistical Methods

All endpoints will be described in term of means and standard deviation, with associated 95% confidence intervals, and median [Q1-Q3]

The change in ICP will be analyzed with a non-inferiority study: the ICP value after intervention will be considered equivalent to the ICP before intervention if the 95% upper bound of the change is lower than the non-inferiority margin of 4 mm Hg.

In a similar manner, the CPP and MAP values before and after intervention will be considered equivalent if the 95% lower bounds of the respective changes are higher than -10 mm Hg.

Should the 95% upper bounds of ICP be higher than 4, the effect of the intervention would be considered inconclusive. Similarly if the equivalence of CPP and MAP cannot be observed, the intervention will be reported inconclusive for these endpoints.

Adverse events will be reported.

By study design, all patients will be monitored in the ICU for the duration of the study and missing values are not expected. However, in the unlikely event that missing values would be present, the subjects will not be excluded and statistics will be calculated on all available data. The dataset for analysis will consist of all subjects regardless of protocol deviation, as an Intent-to-treat population.

Additional data points from the table above will be collected and tabulated using mean and standard deviation.

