6.4 Sample Size and Power

Based on a non-inferiority trial design using a one-sided 95% confidence interval, a power of 80%, a non-inferiority limit of 4 mm Hg for ICP, and a standard deviation of 4.4 mm Hg based on previously published data (11), the study will need 15 participants who require a change in PEEP based on esophageal balloon measurements. To evaluate our secondary goals, using a non-inferiority limit of 10 mm Hg for CPP and a standard deviation of 11.3, we would need 16 subjects, and using a non-inferiority limit of 10 mm Hg for MAP and a standard deviation of 11.8, we would need 18 subjects.

Since we estimate that 29% will not need a change in PEEP (2), we expect we will need to enroll 25 participants and obtain esophageal balloon pressure measurements in order to have 18 participants requiring changes in PEEP.

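### The analysis dataset is all enrolled subjects, although the study is sized on the 18 who need more PEEP; the other 7 or so can enter the three non-inferiority tests and dilute any harm

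*Combined protocol and SAP*

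**What the plan says.** Section 6.3 defines one population for every analysis: "The dataset for analysis will consist of all subjects regardless of protocol deviation", labelled intent-to-treat. Subjects with missing values are kept, and statistics use whatever data are available.

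The recruitment and sample size sections have a narrower group in mind:

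- Section 3.2: "Enrollment will continue until 18 subjects have been enrolled who require an increase in PEEP of at least 5 cm" H2O. About 25 patients are to be measured to find those 18, because a prior study "found 29% of participants were within 5 cm" H2O of optimal PEEP.
- Section 6.4, for ICP: "the study will need 15 participants who require a change in PEEP based on esophageal balloon measurements". The figures for CPP and MAP are 16 and 18. It then says: "Since we estimate that 29% will not need a change in PEEP".

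Other sections bear on who has an endpoint:

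- Section 4.4: "Measurements of ICP, CPP, and MAP will be repeated 5 minutes after the change in PEEP".
- The section 5 table schedules post-intervention ICP, CPP and MAP without restriction. Its only footnote concerns the 24-hour column: "Hourly data collected in patients who are continued on" the titrated PEEP.
- Section 6.1 mentions a target population but does not define it: "the parameter representing mean increase during/after titration is > 4 (mm Hg) in the target population".
- The synopsis and section 1.2 have all patients undergo titration.

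**The concern.** The clinical worry is that raising PEEP raises ICP and lowers CPP and MAP. The sample size is built on patients in whom PEEP has to go up. If patients who get little or no increase are averaged in, the mean change shrinks toward zero and each confidence bound moves toward its success region. The trial could then report safety partly because over a quarter of its patients were barely exposed.

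An intent-to-treat label does not help here. This is a single-group before-after comparison with no randomisation to protect, and in a non-inferiority test the inclusion of unexposed patients favours success.

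The text also leaves room for choice once data exist. A patient with no PEEP change has no moment from which section 4.4 can time the repeat reading, yet section 5 schedules one and section 6.3 uses all available data. Whether such a patient counts could turn on whether a second reading happened to be recorded.

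**Working it through.** **Inputs.** From section 6.4: one-sided 95% interval, 80% power; margins 4 (ICP), 10 (CPP) and 10 (MAP) mm Hg; SDs 4.4, 11.3 and 11.8; 29% needing no change. From section 3.2: 18 patients needing an increase, about 25 in all.

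**The plan's own figures.** With z(0.95) + z(0.80) = 2.486, (SD × 2.486 / margin)² is 7.48 for ICP, 7.89 for CPP and 8.61 for MAP. Doubling gives 14.96, 15.79 and 17.22, which round up to the stated 15, 16 and 18. The stated numbers therefore reproduce only with a doubled variance. For an analysis of within-patient change, this corresponds to change SDs of 4.4 × √2 = 6.2, 11.3 × √2 = 16.0 and 11.8 × √2 = 16.7. The documents do not say which SD applies to the change, so both are used below. Enrolment: 18 / (1 − 0.29) = 25.4, and 25 × 0.29 = 7.25, so about 7 of 25 lie outside the group the study was sized on.

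**Dilution of the mean.** If the 7 show no change, the pooled mean is 18/25 = 0.72 of the mean in the 18. A true rise of 4 appears as 4 × 0.72 = 2.88 mm Hg. The pooled mean reaches the ICP margin only when the rise in the 18 is 4 / 0.72 = 5.6 mm Hg, and the CPP or MAP margin only at a fall of 10 / 0.72 = 13.9 mm Hg.

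**Chance of declaring non-inferiority when the 18 sit exactly at the margin.** Simulation, 400,000 trials per case, normal changes, same SD in both groups. Success for ICP means mean + t(0.95, n − 1) × SD / √n is below the margin; CPP and MAP are handled in the same way for falls. With the 18 alone the result is 5% in every row.

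| Test (assumed SD of change) | Mean change in the 7, mm Hg | 18 + 7 pooled |
|---|---|---|
| ICP (3) | 0 / +1 / +2 / +3 | 45 / 33 / 21 / 11% |
| ICP (4.4) | 0 / +1 / +2 / +3 | 29 / 21 / 14 / 9% |
| ICP (6.2) | 0 / +1 / +2 / +3 | 20 / 15 / 11 / 8% |
| CPP (11.3) | fall of 0 / 2.5 / 5 / 7.5 | 28 / 21 / 14 / 9% |
| MAP (11.8) | fall of 0 / 2.5 / 5 / 7.5 | 27 / 20 / 14 / 9% |

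At the larger SDs of 16.0 and 16.7, CPP and MAP start at about 20% and 19% with the 7 at 0, and end at 7% to 8% with the 7 at a fall of 7.5.

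**Worked bound, ICP, observed mean of +3 in the 18.** With SD 4.4 and the 18 alone: 3 + 1.740 × 4.4 / √18 = 4.80, which fails. Add 7 patients at 0:

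- mean = 54 / 25 = 2.16
- sum of squares = 23 × 4.4² + (18 × 7 / 25) × 3² = 445.28 + 45.36 = 490.64
- SD = √(490.64 / 24) = 4.52
- bound = 2.16 + 1.711 × 4.52 / 5 = 3.71, which passes

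With the 7 at +1 the bound is 3.95 (passes); at +1.5 it is 4.07 (fails). With SD 6.2 the test fails either way: 5.55 alone and 4.30 with the 7 at 0.

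**The case against.** The strongest reply is that the endpoint is tied to titration. Section 6.1 measures it after titration, section 4.4 times it from the PEEP change, and section 6.4 counts only patients who require a change. On that reading an untitrated patient has no endpoint, and the sentence in section 6.3 is about protocol deviations, which being already at target is not. This is a fair account of what may have been intended, but the text does not say it, and the synopsis, section 1.2 and section 5 titrate and measure everyone. Section 3.2 also describes the 29% as within 5 cm H2O of optimal, so some would get a small increase and a valid reading while lying outside the 18.

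A second reply is that section 2 asks about the safety of the guided strategy, which includes finding that some patients need little change. That makes the all-patient result worth reporting. It does not make it a substitute for the test the study was sized for.

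Third, the size depends on assumptions. The largest figures take the 7 at zero change; if some receive a small increase the inflation is lower, though every case examined stays above 5%. Setting the true rise at the margin is how the error rate of a non-inferiority test is defined; it is not a forecast, and section 1.3 cites studies with small or no ICP increases. Section 7.2 also reports large individual changes as adverse events, which limits how far harm could be hidden but does not correct the mean.

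Finally, a cut at 5 cm H2O drops patients raised by less from the confirmatory test. Any PEEP increase would be another reasonable boundary. The 5 cm H2O rule is preferred because section 3.2 already uses it to count the 18.

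**Conclusion.** The concern holds. Section 6.3 admits all subjects, sections 3.2 and 6.4 are built on 18 of about 25, and no section reconciles the two. With the 18 exactly at the ICP margin, pooling raises the chance of a false non-inferiority finding from 5% to between 9% and 29% (SD 4.4) or between 8% and 20% (SD 6.2); CPP and MAP behave alike. These ranges assume normal changes, equal SDs in the two groups, and a mean ICP change in the 7 of 0 to +3 mm Hg (a fall of 0 to 7.5 for CPP and MAP), none of which the documents give. The direction does not depend on the exact values so long as the 7 respond less than the 18. The conclusion of the trial would not always change, as the SD 6.2 example shows. The text is ambiguous rather than certain to mislead, so this should be corrected, but it does not invalidate the design.

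**What to change.** - **Section 6.3:** state that the ICP, CPP and MAP tests use patients whose baseline end-expiratory transpulmonary pressure requires a PEEP increase of at least 5 cm H2O, as in section 3.2. Classify them before any post-titration value is recorded, and keep them in the test even if titration stops early. Report all enrolled patients as a supporting analysis.
- **Section 4.4:** say when the repeat reading is taken in a patient whose PEEP does not change.
- **Minor wording:** in the synopsis and sections 1.2 and 4.3, say that PEEP is only raised and that patients at or above target keep their setting; in section 6.4, refer to an increase rather than a change.

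The cost is a few sentences. PEEP and transpulmonary pressure are already collected under section 5, and recruitment still stops at 18. The downside is that about 7 of 25 patients (28%) leave the primary test and the bounds may be less favourable. With 18 patients and a true change of 0, ICP power is 98% at SD 4.4 or about 84% at SD 6.2. At the doubled variance behind section 6.4, CPP power is 82% and MAP power 79%, close to the planned 80%.

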6.4 Sample Size and Power

Based on a non-inferiority trial design using a one-sided 95% confidence interval, a power of 80%, a non-inferiority limit of 4 mm Hg for ICP, and a standard deviation of 4.4 mm Hg based on previously published data (11), the study will need 15 participants who require a change in PEEP based on esophageal balloon measurements. To evaluate our secondary goals, using a non-inferiority limit of 10 mm Hg for CPP and a standard deviation of 11.3, we would need 16 subjects, and using a non-inferiority limit of 10 mm Hg for MAP and a standard deviation of 11.8, we would need 18 subjects.

Since we estimate that 29% will not need a change in PEEP (2), we expect we will need to enroll 25 participants and obtain esophageal balloon pressure measurements in order to have 18 participants requiring changes in PEEP.

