1.2 Description of Intervention

Trial participants will have placement of an esophageal balloon with manometry capabilities. Baseline measurements of P_{tp} , ICP, CPP, and MAP will be made at their baseline PEEP measurement. All patients will then undergo titration of PEEP based on P_{tp} measurements to an “ideal PEEP” with end expiratory P_{tp} of 0-2. Measurements of ICP, CPP, and MAP will be taken 5 minutes after the intervention. Data will be compared before and after intervention. At the conclusion of the intervention, PEEP management will return to the primary team. In patients continued on the “optimal” level of PEEP, patient data will be monitored for an additional 24 hours in order to report any possible adverse events.

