1.3 Background (Relevant Literature and Data)

The use of PEEP in mechanical ventilation (MV) is important to reduce the collapse of alveoli between breaths. This atelectasis increases the patient’s work of breathing and impairs oxygenation. In addition, atelectrauma can lead to ventilator-induced lung injury (VILI) through repetitive shear injury (1). There is a patient-specific response to PEEP titration, but PEEP titration is frequently not guided by individual patient data. There is a growing body of evidence that titrating PEEP according to estimated transpulmonary pressure (P_{tp}) measurements obtained by an esophageal balloon can improve outcomes, including measurements of lung function and time to liberation from tracheostomy in obese patients requiring prolonged mechanical ventilation, but also with trends toward decreased mortality and less time on the ventilator in survivors of ARDS (2-4). These trials, as well as an ongoing multicenter trial using an esophageal balloon to titrate PEEP in patients with ARDS, have excluded patients with elevated intracranial pressure (ICP) or conditions where hypercapnia-induced elevations in intracranial pressure should be avoided [including intracranial bleeding, cerebral contusion, cerebral edema, mass effect (midline shift on CT scan), flat EEG for ≥ 2 h] for theoretical concerns of increasing ICP and decreasing cerebral perfusion pressure (CPP) (5). Contrary to these concerns, small studies evaluating use of PEEP in this patient population have shown that cerebral autoregulation is improved or unchanged while increases in ICP are small or nonexistent (6-10). Increases in PEEP without guidance of an esophageal balloon in one study caused a clinically insignificant rise in ICP in patients with normal ICP at baseline, however patients with elevated ICP (> 15 mm Hg) at baseline saw no increase in ICP as PEEP was increased (11). Additionally, one case cohort study showed improved hypercapnia with use of esophageal balloon to guide PEEP (3).

This protocol seeks to evaluate the safety of titrating PEEP to “optimal PEEP” based on P_{tp} as measured by and esophageal balloon in patients requiring MV who have CPP or ICP monitoring in place.

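### The sample sizes and 80% power in section 6.4 fit a two-group comparison and do not follow from the single-arm, before/after design under the assumptions stated

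*Combined protocol and SAP*

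**What the plan says.** Section 6.4 describes its basis as "Based on a non-inferiority trial design using a one-sided 95% confidence interval, a power of 80" per cent. For the primary endpoint it combines "a non-inferiority limit of 4 mm Hg for ICP" with "a standard deviation of 4.4 mm Hg based on previously published data (11), the study will need 15 participants". For CPP it uses a margin of 10 mm Hg and an SD of 11.3 to reach 16. For MAP the wording is "using a non-inferiority limit of 10 mm Hg for MAP and a standard deviation of 11.8, we would need 18 subjects". The largest of the three, 18, becomes the target for participants who need a PEEP change, and allowing for 29% who do not, about 25 are to be enrolled.

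The rest of the plan describes one group measured twice. The synopsis (Study Design) has every patient titrated, and section 1.2 says "Data will be compared before and after intervention". Section 6.1 states "The primary endpoint is change in ICP 5 minutes after PEEP titration". Section 6.3 declares success "if the 95% upper bound of the change is lower than the non-inferiority margin of 4 mm Hg", with a matching lower bound of -10 mm Hg for the changes in CPP and MAP.

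Section 6.4 does not name a formula. It does not say whether the SDs describe single readings or changes, and it gives neither a before/after correlation nor an expected true change.

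**The concern.** In a one-sample analysis of change, the required size depends on the SD of the change and on the distance between the margin and the true mean change. Section 6.4 pins down neither, and its three sizes coincide with those for a different design, two independent groups.

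The target of 18, the enrolment of about 25 and the 80% power claim all rest on this calculation. As written, a reader cannot tell what power 18 subjects give, or how large a true ICP rise the trial can tolerate before it is likely to miss its bound. Section 6.3 reports a missed bound as inconclusive, so this tolerance matters for interpreting the result.

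Zero true change cannot simply be presumed. Section 1.3 reports that raising PEEP without balloon guidance "in one study caused a clinically insignificant rise in ICP in patients with normal ICP at baseline", citing reference 11, which is also the source of the ICP SD. The same sentence reports no rise in patients whose baseline ICP was above 15 mm Hg. The exclusion limit is 20 mm Hg, so both kinds of patient are eligible.

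**Working it through.** **Inputs (section 6.4).** One-sided alpha 0.05 (z = 1.645); power 80% (z = 0.842); margins M = 4/10/10 mm Hg; SDs s = 4.4/11.3/11.8 mm Hg, in the order ICP/CPP/MAP. The squared sum of the z values is (1.645 + 0.842)² ≈ 6.18. The ratios (s/M)² are 1.2100, 1.2769 and 1.3924.

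**Step 1: reproduce the plan's figures.** Two independent groups, zero true difference, n per group = 2 × 6.18 × (s/M)²:

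- ICP: 14.96, rounded up to 15
- CPP: 15.79, rounded up to 16
- MAP: 17.22, rounded up to 18

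All three match exactly.

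**Step 2: the design in the plan.** One sample of changes, s taken as the SD of change, zero true change, n = 6.18 × (s/M)²: 7.48, 7.89 and 8.61, so 8/8/9. With the noncentral t distribution the sizes are 9/10/11. Power at the plan's 15/16/18 is then 95.5/95.8/96.4%, and at 18 it is 98.0/97.5/96.4%.

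**Step 3: single-reading SDs.** The SD of change is then s × √(2(1 − ρ)). The correlation ρ is not in the documents, so these values are assumptions. Zero true change, t-based:

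| ρ | Required n | Power at 15/16/18 | Power at 18 |
|---|---|---|---|
| 0 | 17/18/19 | 76.5/77.1/78.6% | 83/82/79% |
| 0.3 | 12/13/14 | 88.1/88.6/89.8% | 93/92/90% |
| 0.5 | 9/10/11 | 95.5/95.8/96.4% | 98/97/96% |

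At ρ = 0 the SD of change is s√2, so the normal one-sample formula becomes identical to the one in step 1 and returns 15/16/18.

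**Step 4: a non-zero true change.** With s as the SD of change and a true worsening d, n = 6.18 × s²/(M − d)². This returns 15, 16 and 18 for d of about 1.1 mm Hg (ICP), 2.7 to 3.0 (CPP) and 2.9 to 3.1 (MAP). The documents give no value of d, so the rows below are scenarios (ICP, SD of change 4.4, t-based):

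| True ICP rise (mm Hg) | Power at 18 | n for 80% power |
|---|---|---|
| 0 | 98% | 9 |
| 0.5 | 94% | 12 |
| 1 | 87% | 15 |
| 1.5 | 75% | 21 |
| 2 | 58% | 32 |

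For CPP/MAP, power at 18 is 89/87% with a 2 mm Hg fall and 81/78% with a 3 mm Hg fall. On this basis, 18 subjects keep 80% power up to a true ICP rise of 1.3 mm Hg, a CPP fall of 3.1 and a MAP fall of 2.8. If 4.4 is instead a single-reading SD with ρ = 0, a 1 mm Hg ICP rise leaves 62% power at 18.

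**The case against.** The strongest reply is that the match in step 1 proves less than it seems to. A paired normal calculation with single-reading SDs and zero correlation is algebraically the same formula, so 15/16/18 may come from a paired calculation with a cautious correlation. On that view section 6.4 is incomplete rather than wrong. Moreover, nothing bad follows at zero true change: ICP power at 18 is at least 83%, and the lowest figure for any endpoint is 79%, for MAP with ρ = 0. Zero correlation is also hard to believe for ICP readings taken close together in patients excluded for more than 2 cm H₂O variation over 15 minutes. Finally, section 1.3 calls the reported ICP rise clinically insignificant and gives no size, and section 6.3 analyses all subjects, so the number analysed could be about 25 rather than 18.

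Much of this stands. The documents cannot show which formula was used, the mismatch is mostly conservative, and the ICP rises in step 4 are illustrations only. Power at 18 follows section 6.4's own basis of participants who need a PEEP change. With 25 analysed and the same SD, ICP power at ρ = 0 and zero change would be 93%, although patients whose PEEP was not changed could also dilute the mean change.

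The reply does not rescue the stated figures. Each route from a paired design at one-sided 5% and 80% power to 15/16/18 needs an assumption that section 6.4 does not state. The zero-correlation route also falls slightly short of 80% once the t distribution is used.

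**Conclusion.** The sizes and the 80% power do not follow from the single-arm paired design under the assumptions section 6.4 states. With SDs of change and zero true change, the plan's sizes exceed what is needed by 6 to 7 patients per endpoint (15 against 9, 16 against 10, 18 against 11).

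This is not a finding that the trial is underpowered for ICP at 18. The finding is that the power is undetermined. At zero true change, ICP power at 18 runs from 83% to 98% over correlations of 0 to 0.5. It drops below 80% once the true rise exceeds about 1.3 mm Hg, even if 4.4 is the SD of change. These figures assume normally distributed changes, a one-sided 5% test and 18 analysed subjects. The decision rule in section 6.3 is unaffected.

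**What to change.** Rewrite section 6.4 as a one-sample (paired) non-inferiority calculation on the within-patient change, using the t distribution. For each endpoint, state:

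1. the SD of change, or the single-reading SD with an assumed before/after correlation;
2. the assumed true mean change;
3. the required n;
4. the power at 18 over a range of true changes, for example ICP rises of 0, 0.5, 1, 1.5 and 2 mm Hg and CPP and MAP falls of 0 to 3 mm Hg.

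If the source confirms that the SDs are SDs of change, the figures in steps 2 and 4 can be used, each with its assumed true change beside it. Add a sentence saying that the power refers to participants who need a PEEP change, whereas section 6.3 analyses all subjects.

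The cost is text and figures in section 6.4 only. The target of 18, enrolment, procedures and the section 6.3 decision rule do not change.
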